To ensure treatment fidelity, three to four sessions will be randomly audio-recorded per intervention group to make up a full program for progress evaluation and commented by an experienced psychiatrist who has been practicing mindfulness and cognitive therapy for over 10 years based on the validated manualized protocol and the Mindfulness-Based Interventions Teaching Assessment Criteria (MBI:TAC) (Crane et al, 2013). The attendance and dropping-out of patients in both treatment and active control group will be continuously monitored by the researcher.

Outcome Evaluation

The primary outcome will be the Depression Anxiety Stress Scale- Short form (DASS-21) (Lovibond & Lovibond, 1995). It is chosen as the primary outcome measurement because scales of anxiety and depression possess the capacity to differentiate from the related state of tension and stress linking with environmental demands and emotional and physical disturbance. It is a 21-item instrument that measures over the past week symptoms of depression, anxiety and stress rated by 4-point severity or frequency scale. The scale is from 0 (did not apply to me at all) to 3 (applied to me very much or most of the time). Internal consistency for each scale for the DASS normative sample are as follows: Depression $\alpha=0.91$; Anxiety $\alpha= 0.84$; Stress $\alpha=0.90$. The phi coefficients of the Chinese DASS-21 version are as follows: Beck Depression Inventory and Beck Anxiety Inventory are Depression-Anxiety 0.81; Anxiety-Stress 0.88 and Depression-Stress 0.83 (Moussa, Lovibond and Laube, 2001).

The secondary outcome measures will be including:

The Emotion Regulation Questionnaire (ERQ) (Gross and John, 2003) is a 10-item scale that was developed to measure participants' tendency to regulate their emotions in cognitive reappraisal and expressive suppression. Items are scored on a 7-point Likert scale ranging from 1 (strongly disagree) to 7 (strongly agree). The internal consistency reappraisal items are from $\alpha= 0.75 - 0.82$ while suppression items are from $\alpha= 0.68 - 0.76$. The reliability for reappraisal and suppression is $\alpha=0.79$ and $\alpha=0.73$ respectively.

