Mediation analyses will be conducted to examine covariates of change in emotions and distress associated with psychotic symptoms by multiple regression analysis. Within – subjects effect sizes will also be reported based on Cohen's d statistic. Kaplan Meier survival analysis will be used for the analysis of re-hospitalization rates across treatment and control groups. The significance level of all statistical tests will be set at 5%. Clinical significance will be all subscales of DASS-21 shows a percentage improvement in mean scores in the range of approximately 45–55% pre- and post-intervention (Ng, Trauer, Dodd, Callaly, Campbell and Berk, 2007). For example, the mean DASS severity ratings of depression in pre-intervention is 31.2 and 16.2 in a week post-intervention. The difference is 15.0 and the percent change is 48.1 which is clinical significant. Reliable Change Index (RCI) will take into account the reliability of assessment instrument on scores of each participant between the pre-test and one post-test divided by the standard error of the difference between the two scores. Any value of RCI >1.96 (at p<0.05) will be considered statistically significant (Jacobson & Truax, 1991).

NVivo will be used to analyze the qualitative data on subjective experiences to mindfulness and acceptability to the interventions (Krippendorff, 2004). All audio-taped interviews will be transcribed into Cantonese/Chinese by the research assistant and checked for accuracy of transcription by the researcher. The revised transcripts

will be coded independently and important manifest and meanings in the data will be identified.

Ethical considerations

Approval for human subject research will be obtained from the three ICCMWs and Edinburgh Napier University before the start of data collection. The researcher will ensure and inform the potential participants that participation in the study is voluntary and that withdrawal from the study at any time will not affect any aspects of care. The information leaflet and consent form will be developed according to the format recommended by School of Health and Social Care ethics committee. All participants will be assured of the confidentiality of the data provided and the anonymity of their personal identity, and asked for permission to tape record the interviews and intervention sessions if selected. All data will be safely kept in a locked cabinet accessible only by the researcher.

Adverse events reporting and monitoring

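### The DASS-21 clinical-significance rule is a 45–55% range with an upper end, so larger improvements miss the label; it also leaves open whether the label is joint or per subscale

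*SAP*

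**What the plan says.** The SAP names DASS-21 as the primary outcome under Outcome Evaluation and describes it there: "It is a 21-item instrument that measures over the past week symptoms of depression, anxiety and stress". That gives three subscales.

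Under Data Analysis it sets a group-level criterion: "Clinical significance will be all subscales of DASS-21 shows a percentage improvement in mean scores in the range of approximately 45–55" per cent between the pre- and post-intervention means. A worked illustration follows at once: "the mean DASS severity ratings of depression in pre-intervention is 31.2 and 16.2 in a week post-intervention". Its conclusion is: "The difference is 15.0 and the percent change is 48.1 which is clinical significant". No anxiety or stress figures are shown.

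The next sentences add a Reliable Change Index, calculated for each participant: "Any value of RCI >1.96 (at p<0.05) will be considered statistically significant". The SAP says nowhere how a mean improvement above 55% is to be classed, or whether the label needs the three subscales together or is given to each in turn.

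**The concern.** There are two faults of wording, and the first is the more serious.

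1. **Upper end.** A criterion for benefit should be one-sided: if 50% is enough, 60% should be. The written rule stops at about 55%, so a better result can lose the label that a weaker one earns.

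2. **Joint or per subscale.** The rule speaks of all subscales, but the example attaches the verdict to depression with nothing said about the other two. A reader cannot tell whether one subscale can carry the label.

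This is the only group-mean threshold of clinical significance that the plan sets for its primary outcome measure. If it stays open, the label can be granted or withheld by choosing a reading once the results are known.

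**Working it through.** **Inputs from the SAP.** Range of approximately 45–55%; example means 31.2 and 16.2 (both Data Analysis); three subscales (Outcome Evaluation); 41 participants per group before attrition (Sample size).

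**Step 1: reproduce the plan's figure.** Percentage improvement = (pre − post) / pre × 100 = (31.2 − 16.2) / 31.2 × 100 = 15.0 / 31.2 × 100 = 48.08%. The stated 48.1% is right and lies inside the range.

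**Step 2: turn the range into post-intervention means at the same baseline.**
- 45% improvement: 31.2 × 0.55 = 17.16
- 55% improvement: 31.2 × 0.45 = 14.04
- 60% improvement: 31.2 × 0.40 = 12.48, outside the range
- 70% improvement: 31.2 × 0.30 = 9.36, outside the range

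As a floor of 45%, the rule would admit every post-intervention mean of 17.16 or lower.

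**Step 3: apply the readings to illustrative sets of improvements** (assumed figures, in the order depression / anxiety / stress).

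| Improvements (%) | All three in 45–55% | Depression in 45–55% | All three at least 45% |
|---|---|---|---|
| 48.1 / 50 / 46 | yes | yes | yes |
| 48.1 / 30 / 30 | no | yes | no |
| 60 / 60 / 60 | no | no | yes |
| 70 / 50 / 50 | no | no | yes |

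The second row shows the joint versus per-subscale question. The last two rows show the upper-end problem.

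**Step 4: how often this would bite.** The SAP gives no standard deviations or correlations, so the following are assumptions: 41 in an arm with both measurements; subscale SD 0.5 to 0.8 of the baseline mean; pre–post correlation 0.5; correlation 0.8 between subscales; the same true improvement on all three. The log of the post/pre ratio of means is treated as normal, with

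SE = √[(a² + b² − 2 × 0.5 × a × b) / 41],

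where a and b are the SD divided by the mean before and after.

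- SD shrinking in proportion to the mean, a = b = 0.6: SE = √(0.36 / 41) = 0.094.
- SD constant in raw points, true improvement 60%: b = 0.6 / 0.4 = 1.5, so SE = √[(0.36 + 2.25 − 0.90) / 41] = √(1.71 / 41) = 0.204.

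At a true improvement of 60%, across both treatments of the SD and SD/mean from 0.5 to 0.8, all three subscales fall in the 45–55% range about 2–8% of the time. All three reach at least 45% about 80–100% of the time.

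At a true 50% the result depends heavily on the SD assumption. With SD/mean 0.6, the range is met 53% of the time if the SD shrinks with the mean and 21% if it stays constant. No single percentage should therefore be quoted as the size of the problem.

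**The case against.** The strongest reply is that the author plainly meant a benchmark and would never deny the label to a 60% improvement. The word approximately also softens both ends. Part of this stands: 55% is not a hard cut-off, 44% or 56% is undecided, and a minimum was probably intended. But the text does not say so, and softened ends do not stretch to 60% or 70%.

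The second reply is that the example is only an illustration of the calculation for one subscale, and that all subscales may mean that the yardstick applies to each. This stands. A reader might infer that rule and example contradict each other, but the SAP does not say that depression alone suffices for an overall label. It is an ambiguity, and it still needs settling.

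A reader might also infer that the example is impossible on this scale. With 21 items scored 0–3 and split equally over three subscales, the maximum is 7 × 3 = 21, below 31.2 unless scores are doubled. That is no ground for this point. Doubling cancels in a percentage, and the scoring metric has no bearing on range versus floor or on joint versus separate use.

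Finally, the Reliable Change Index could be offered as the real measure of meaningful change. It is a separate criterion for individual participants, and the plan calls its result statistically significant. It does not repair the group-mean rule.

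**Conclusion.** The point holds as a defect in a stated threshold. As written, mean improvements well above 55% fail a label that 50% earns, and nothing else in the SAP corrects this. That conclusion needs only the rule's own wording and the arithmetic of Step 2. The 2–8% against 80–100% at a true 60% improvement rests on the assumptions of Step 4 and indicates scale only. Joint versus per-subscale use is a lesser ambiguity.

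A reader might conclude that the trial's main inference is at risk. The SAP does not support that: inference is by repeated-measures ANOVA at the 5% level, and this label enters neither the test, nor the significance level, nor the sample size. The point should be corrected before the data are seen, but it concerns interpretation only.

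**What to change.** In the Data Analysis section of the SAP:

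1. Restate the range as a minimum: a mean improvement of at least 45% from before to after the intervention. This is the lower edge of the plan's own range. If the sponsor prefers another floor, it should justify it from the source that it cites.
2. State, before data are seen, which of two uses applies: one label requiring all three DASS-21 subscales to reach the floor, or a separate label for each subscale with all three verdicts reported.
3. Align the example. For a joint label, show depression, anxiety and stress together. For separate labels, say that the example's verdict concerns depression only.

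The cost is a few sentences of wording. No new data, further analysis or change to the sample size is needed.

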Two groups of 3-4 participants in treatment group will be interviewed in a quiet interview room in the ICCMWs, or as preferred by the participants. Participants with significant positive changes, minimal changes and negative changes will be invited according to the baseline and Post-test 1 measurement. Interviews in a focus group format will be conducted to identify the strengths and limitations and therapeutic components from the participants' perspective. Interview questions will be developed based on an open and broad basis criterion (Appendix 2). Audio-recorded group sessions will also be used to examine the group process/dynamics and participants' involvement and appraisals of the group program.

The outcome measurements will be completed by the participants at three and six months after the interventions with the help of RA1 who will be blind to the participants' assigned groups. By self-reporting or case files reviewing, re-hospitalizations of the participants will also be examined and calculated and checked against their medical records. Participants' recruitment, interventions, data (outcomes) collection, and data analyses are outlined in a flow diagram of Appendix 3, as recommended by the latest CONSORT statement.

Data Analysis

Intention-to-treat (ITT) analyses (Fisher et al, 1989) will be used to provide a more conservative estimate of outcomes. By using IBM SPSS, version 23.0, all data on participants' socio-demographic illness-related characteristics, attendance and completion rate, and study outcomes will be numerically coded, summarized and analyzed. Repeated-measures ANOVA tests will be used to assess any significant differences on all dependent (outcome) variables within and between groups and across three post-tests (one week, 3 months and 6 months follow-up).

Sub-group analysis for participants who will complete all sessions and those completers, and the outliers which can have deleterious effects on statistical analyses will also be screened. Defined completers will be those who have attended at least eight sessions by which the main themes of the program are covered (Nose, Barbui and Tansella, 2003).

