All adverse events will be recorded according to criteria stipulated by the Research Ethics Committee of ICCMWs and Edinburgh Napier University. It may be including potential adverse events of meditational practices such as meditation related depersonalization, derealization and disturbing psychotic symptoms (Sharma, Gupta and Sagar, 2015), and feelings of intense anxiety and depression. A trained professional on the research team will be present to advise the participant and provide ad hoc psychological support. Each event will be examined by an independent panel which includes expert clinicians in the area of psychosis to minimize the risk of bias in the critique to whether the adverse event is interrelated or not to meditation. Furthermore, participants on trial with a PANSS 25% or more deterioration and demonstrating unexpected effects will be reported (Leucht et al, 2005).

Potential implications/significance of the study

Several small, non-randomised controlled studies have supported that mindfulness interventions for individuals with psychotic disorders specifically in treating negative symptoms is feasible and effective. This randomized controlled study will further confirm previous findings, test for generalization by using a standardized and validated intervention protocol and investigate potential moderators (e.g. attention regulation, acceptance, body awareness, cognitive appraisals) of mindfulness-based intervention in managing emotional dysregulation and symptoms.

References

Altaman, D.G. & Bland, J.M. (1999) Statistics notes. Treatment allocation in controlled trials: Why randomize? *BMJ*. 318,1209.

American Psychiatric Association. (2013) *Diagnostic and Statistical Mental Disorders DSM-V (5thEd.)*. American Psychiatric Association.

Beck, A. T., Rector, N. A., Stolar, N. & Grant, P. (2009) *Schizophrenia: Cognitive theory, research and therapy*. New York, Guilford.

Birchwood, M. (2003) Pathways to emotional dysfunction in first-episode psychosis. *British Journal of Psychiatry*. 182, 373–375.

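### The SAP names intense anxiety and depression as possible harms but sets a measured deterioration rule only on PANSS, and its per-participant DASS-21 change index never counts who got reliably worse in each arm

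*SAP*

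**What the plan says.** **Adverse events reporting and monitoring.** The section names "feelings of intense anxiety and depression" among the potential adverse events. It has a general recording rule: "All adverse events will be recorded according to criteria stipulated by the Research Ethics Committee of ICCMWs and Edinburgh Napier University". Those criteria are not reproduced in the document. Recorded events go to review: "Each event will be examined by an independent panel which includes expert clinicians in the area of psychosis". The one criterion tied to a scale is that "participants on trial with a PANSS 25% or more deterioration and demonstrating unexpected effects will be reported".

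**Outcome Evaluation.** DASS-21 is the primary outcome: "It is a 21-item instrument that measures over the past week symptoms of depression, anxiety and stress". It is scheduled at baseline, one week, 3 months and 6 months in both arms.

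**Data Analysis.** DASS-21 enters a repeated-measures ANOVA that looks for differences without stating a direction. Clinical significance is defined by improvement in means: "all subscales of DASS-21 shows a percentage improvement in mean scores in the range of approximately 45–55% pre- and post-intervention". The RCI is computed for each participant between the pre-test and one post-test: "Any value of RCI >1.96 (at p<0.05) will be considered statistically significant". No sign convention, worsening category or tabulation by arm is given.

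**Data collection procedure.** Individual worsening is used once, to choose focus-group members from the treatment group: "Participants with significant positive changes, minimal changes and negative changes will be invited according to the baseline and Post-test 1 measurement". This concerns two groups of 3 to 4 people.

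**The concern.** The plan writes a measured deterioration rule for psychotic symptoms and none for the affective harm that it names in the same section, although its primary outcome is a scale for that harm. It also already plans the index that would identify individual participants who worsen, but leaves that index without a harm reading.

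At stake is whether the trial can see a minority who became clearly more depressed or anxious. The ANOVA and the percentage-improvement rule both work on means, and a favourable mean is compatible with a worsened subgroup. The PANSS rule targets a different construct, as the plan itself describes that scale. The report could thus show lower average distress under MBCTp and say nothing about how many participants in each arm moved reliably the other way.

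**Working it through.** **1. Where individual DASS-21 worsening could surface, and whether it is counted as harm**

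| Place in the SAP | What it does | Counts worsening by arm? |
|---|---|---|
| Repeated-measures ANOVA | Compares means, either direction | No |
| 45–55% rule | Improvement in means | No |
| RCI | Per participant, above 1.96, one post-test | No |
| Focus-group selection | 6 to 8 people, treatment arm only | No |
| PANSS 25% rule | Different scale | No |
| Independent panel | Reviews events already recorded | No |

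The RCI rule as written depends on an unstated sign. If improvement is coded positive, a reliably worse participant has an RCI below -1.96 and is not flagged. If the rule is meant for the absolute value, improvers and worseners fall into one group.

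**2. What the RCI would flag if applied to worsening**

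The SAP states no threshold of its own to reproduce. Inputs are its reliabilities from Outcome Evaluation: depression 0.91, anxiety 0.84. Taking internal consistency as the reliability is an assumption.

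SE of a difference = SD × √(2 × (1 − reliability)); threshold = 1.96 × SE.
- Depression: √(2 × 0.09) = 0.424 SD; × 1.96 = 0.83 SD.
- Anxiety: √(2 × 0.16) = 0.566 SD; × 1.96 = 1.11 SD.

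**3. Can a mean hide a worsened minority?**

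The Sample size section gives a design effect of 0.63 SD with 41 per group (a two-sample t-test reproduces the 41, with power 0.805). For illustration, I use 0.63 SD as the within-arm gain of those who improve. Suppose 10% of one arm (about 4 of 41) worsen by 1.5 SD and 90% improve by 0.63 SD:

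0.9 × 0.63 − 0.1 × 1.5 = 0.567 − 0.150 = 0.417 SD mean improvement.

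**4. How many might be flagged?**

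Let individual true change have SD h around the mean gain. The documents do not give h, so I assume 0.5 to 1.0 baseline SD.

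Proportion reliably worse on depression = Φ((−0.83 − mean gain) / √(h² + 0.424²))

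| Mean gain | h = 0.5 | h = 1.0 |
|---|---|---|
| 0.63 SD | 1.3% | 8.9% |
| 0 | 10.2% | 22.2% |

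**5. Chance flags**

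With no true change, about 2.5% exceed the limit in the worsening direction per score and visit. Two scores at three visits make six looks: 1 − 0.975⁶ = 14% of participants flagged at least once if the looks are independent, or about 6 of 41 per arm.

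**6. Precision of the comparison**

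If 10% were flagged in each arm of 41, the SE of the difference is √(2 × 0.10 × 0.90 / 41) = 0.066, so the 95% CI half-width is 1.96 × 0.066 = 0.13, about 13 percentage points. The comparison is descriptive.

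**The case against.** **Detection of the harm.** A reader might infer that intense anxiety or depression would come to light only if somebody happened to notice it. The document does not support that. Adverse events are recorded under ethics-committee criteria that are not shown and that could include active questioning. How events are elicited commonly sits in a protocol. What stands is that this document gives no measured criterion for the affective harm while giving one for PANSS.

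**Use of DASS-21.** A reader might also infer that the scale serves benefit alone. That goes too far: the ANOVA has no stated direction, the RCI has none either, and the focus-group selection looks for negative change. Only the 45–55% rule is restricted to improvement. None of these, however, yields a count of worsened participants by arm.

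**Neutrality of the measure.** Nor can DASS-21 be presented as taken the same way in both arms. Under Data collection procedure, RA1 delivers PEp and, though described as blind, also helps participants complete the 3- and 6-month measures. The proposed table would carry that weakness at two of its three visits.

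**Coverage.** The strongest objection is that the table misses much of the harm in question. DASS-21 looks back one week, and the first post-test is one week after a 12-week programme. Distress that arises and settles during the sessions would leave no trace. Participants who leave because of distress may have no post-test, and the plan allows for 15% attrition. The professional support and panel review in the adverse-events section address the in-session setting better. This objection stands as a limit on the remedy. It does not explain why lasting worsening, which the scale can show, should go uncounted.

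**Size.** The 1% to 22% range rests on an assumed spread of individual change, and flags at no mean change could occur equally in both arms. The reliabilities come from a normative sample, not from people with recent-onset psychosis followed for months. These points are fair. They support a comparison by arm and argue against treating the raw count as proof of harm.

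**Conclusion.** The point holds as a gap in the analysis rules: one named harm has a measured criterion, the other has none, and an index that could fill the gap is planned without a worsening category or comparison by arm. This rests on the text and on no assumption.

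Its size is indicative. The 0.83 and 1.11 SD thresholds assume that the quoted alphas hold in this population. The 0.42 SD mean gain is an illustration that a mean can look good while a tenth of an arm worsens. The proportions in the table depend on the assumed spread of 0.5 to 1.0 SD. No actual excess of harm under MBCTp is shown or implied, and the sample size is unaffected. The change is a worthwhile, inexpensive improvement; the gap does not undermine the efficacy analysis.

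**What to change.** In Data Analysis, define the RCI in both directions with a stated sign: reliably improved, unchanged, reliably worse. Apply it from baseline to each of the three post-tests for DASS-21 depression and anxiety. Tabulate the three categories by arm and visit, with the number assessed, and give the difference in proportions reliably worse with a 95% CI. In the adverse-events section, state that this table is reported beside the PANSS criterion as a descriptive harm summary and not as a trigger for clinical action.

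State four limits with the table:
- about 2.5% chance flags per score and visit, up to about 14% of participants over six independent looks;
- no capture of transient distress during the 12 weeks or of people without a post-test;
- imperfect masking at 3 and 6 months, given RA1's two roles;
- thresholds based on normative-sample reliabilities.

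The cost is a few sentences and one table from data already collected. The index is already planned, but for one post-test; it would be extended to all three. The drawback is a harm report that looks less favourable in both arms, partly by chance, which is why the difference between arms should be shown and not the MBCTp count alone.

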9	Theme: Responding thoughts Activities: early warning activity; 3-minute breathing space; my relapse signature activity; enquiry	Theme: Discontinuing medication Activities: pros and cons; risk of relapse; side-effects; physical health; enquiry
10	Theme: Kindness the healing Activities: mastery and pleasure activity; nourishing and depleting; 3-minute breathing space (regular and responsive); enquiry	Theme: Involuntary treatment Activities: information about and reason for involuntary treatment; legal rights; enquiry
11	Theme: Making a difference Activities: an action plan; 3- minute breathing space (regular); enquiry	Theme: Relapse prevention Activities: introduction; relapse prevention; early warning signs; enquiry
12	Theme: Practice momentum and ending Activities: 10- min body scan; review; personal reflections; plans for practice continuum; closing sitting	Theme: Developing a wellbeing plan Activities: sleep hygiene; managing stress; reducing substance use; keeping healthy; enquiry

[figure not shown]

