Appendix 2 Guidelines to Semi-structured Focus Group Interview

The interview may follow the questions as below:

We are interested in finding out about your experiences of the mindfulness program

Interview Questions	
1	What did you expect from the mindfulness program when you started?
2	Did the program reflect what you expected? How so? How not so?
3	How would you describe what the program is about and what you have learned?
4	What keeps you coming back to and finish the mindfulness program?
5	What do you particularly like about the mindfulness program?
6	What do you dislike or like less about the mindfulness program?
7	What is the most difficult and/or easy mindfulness activity?
8	What is it like using mindfulness? How would you describe mindfulness for you?
9	What have you found helpful or not so helpful about the mindfulness program?
10	How have you been feeling emotionally/physically/socially since the mindfulness program began? Any differences between now and before you joint the program?
11	What difficulties have you experienced in doing the homework?
12	Have you ever experienced any psychotic symptom? If yes, how did you respond to it?
13	In what way do you think that you have benefited from practicing mindfulness?
14	Did you find learning mindfulness in a group to be helpful?
15	What form might the mindfulness practice take place in the future?
16	How do you think people with psychosis should be best supported in community services?
17	What do you think could be done to improve the treatment program? Time, place, duration?
18	Is there anything you would like to mention and we have not covered in our discussion today?

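### The adverse-event panel is asked only about relatedness to meditation, so an event caused by psychoeducation cannot be classed as related to its own intervention

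*SAP*

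**What the plan says.** The SAP section Adverse events reporting and monitoring makes four statements that matter here.

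- Recording covers everything: "All adverse events will be recorded according to criteria stipulated by the Research Ethics Committee of ICCMWs and Edinburgh Napier University".
- Review covers everything: "Each event will be examined by an independent panel which includes expert clinicians in the area of psychosis". Neither statement is limited to one arm.
- The panel's purpose and its question come together: it is there to "minimize the risk of bias in the critique to whether the adverse event is interrelated or not to meditation". No other relatedness question is given.
- The examples start from one arm's content: "It may be including potential adverse events of meditational practices such as meditation related depersonalization, derealization and disturbing psychotic symptoms". The sentence then adds intense anxiety and depression, which are not specific to meditation.

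The section also says that trial participants whose PANSS worsens by 25% or more will be reported.

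The Interventions section gives MBCTp to the study groups and PEp to the control groups. Appendix 1 sets out 12 sessions for each. Body scans, sitting meditation and breathing-space exercises appear only in the MBCTp column. The PEp column covers illness education, treatment, medication adherence (session 8), discontinuing medication (session 9) and involuntary treatment (session 10: "information about and reason for involuntary treatment; legal rights; enquiry").

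**The concern.** The comparator is an active, 12-session group programme, not an absence of treatment. Some PEp topics, such as stopping medication, the risk of relapse and involuntary treatment, could plausibly distress a participant. If that happened, the event would be recorded and reviewed, but the panel could answer only whether meditation was involved. The natural answer is no, and the event would be filed as unrelated even if the PEp session had caused it.

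In MBCTp the same question amounts to asking whether the participant's own intervention was the cause. One arm is therefore asked about its own treatment and the other about a treatment that Appendix 1 does not give it. At stake is the meaning of a related adverse event. In a two-arm trial, readers will look at that count by arm, and the panel was set up to reduce bias in exactly this judgement.

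**Working it through.** The SAP gives no adverse-event rate, harm margin or power for harm, so there is no figure to reproduce. The check is a comparison of the text, followed by a short piece of algebra to show what the size would depend on.

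**Comparison of the text**

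| Question | MBCTp | PEp |
|---|---|---|
| Are adverse events recorded? | Yes, all | Yes, all |
| Does the panel examine each one? | Yes | Yes |
| Is meditation in the session content (Appendix 1)? | Yes | No |
| Can an event be classed as related to meditation? | Yes | Not from session content |
| Can an event be classed as related to its own intervention? | Yes, through meditation | No category exists |

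The last row is the defect. It follows from what the SAP states, not from something it leaves out.

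**Does the home practice change this?** The Interventions section describes both arms and then says that all sessions comprise 12 weekly meetings plus home practice with guided mindfulness CDs. One reading gives the CDs to PEp participants too. On that reading a PEp event could be judged related to meditation, so the fourth row would change. The fifth would not: an event caused by psychoeducation content would still have no category.

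**Which harm measures depend on the panel's answer?**
- The count of related events does.
- The count of all recorded events does not.
- PANSS deterioration of 25% or more does not. The sentence joins it to unexpected effects, so it is unclear whether both are required, but neither is tied to the panel's relatedness answer.
- Re-hospitalization does not. Data Analysis compares it between arms by Kaplan-Meier.

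**What the size would depend on.** Assume the same adverse-event risk q in both arms, the same share s of events truly caused by the allocated intervention, a panel that classifies perfectly, and no meditation in PEp. With n per arm:
- related events in MBCTp = n × q × s
- related events in PEp under the meditation question = 0
- artificial risk difference = q × s
- with an arm-neutral question, both arms give n × q × s and the difference is 0.

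Only n = 48 per group comes from the SAP (Sample size). Both q and s are assumptions:
- low end, q = 0.10 and s = 0.25: 48 × 0.10 × 0.25 = 1.2 events against 0, a gap of 2.5 percentage points
- high end, q = 0.40 and s = 0.50: 48 × 0.40 × 0.50 = 9.6 events against 0, a gap of 20 percentage points.

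The all-cause counts (48 × 0.10 = 4.8 to 48 × 0.40 = 19.2 per arm) are equal between arms under either wording. The range shows only that the gap is the product of two quantities the document does not supply. It does not estimate what this trial would see.

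**The case against.** The strongest reply is that the SAP plans no comparison that this would spoil. Data Analysis applies repeated-measures ANOVA to the outcome variables and Kaplan-Meier to re-hospitalization. Adverse events appear only under reporting and monitoring, and all of them are captured whatever the panel decides. This stands. A reader might infer that a planned between-arm harm comparison is distorted by construction, but the document contains no such comparison. What remains is that relatedness is the only panel output described, it is lopsided, and no by-arm tabulation of all events is specified to set beside it.

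A second reply is that the ethics committee criteria, or a protocol not at hand, may define relatedness more fully. They may, but the SAP cites those criteria for recording events and states the panel's question itself.

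Three stronger readings are tempting and are not supported.
- *The panel is unblinded.* The SAP does not say whether the panel knows the allocation. The meditation question invites it to guess, but to conclude that it is unmasked is to argue from silence on a matter that may be settled elsewhere.
- *The focus groups inflate harms in MBCTp.* They are held only in the treatment group, and Appendix 2 asks about psychotic symptoms. But they are a qualitative exercise in two groups of 3-4 people, and nothing in the SAP feeds their content into the adverse-event record.
- *The bias runs against MBCTp.* A panel reluctant to blame meditation could equally put MBCTp events down to the illness. The missing PEp category is fixed by the wording; the net direction of the panel's judgements is not.

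**Conclusion.** The point holds in a limited form. The panel's relatedness question fits one arm only, so an event caused by PEp cannot be attributed to PEp, and counts of related events by arm would not be comparable. This falls short of the panel's stated aim of reducing bias. The conclusion rests on the panel's question being as the SAP words it and on Appendix 1 showing where meditation is delivered. It survives the reading in which the home-practice CDs reach both arms.

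The consequence is confined to harm attribution. Efficacy estimates, type I error and power are untouched, as are the harm measures that need no attribution. The size cannot be derived from the document. The change is worth making because it is cheap and removes a real one-sidedness, but the trial's main conclusions do not depend on it.

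**What to change.** 1. Replace the panel's question with one that reads the same for both arms: is the event related to the allocated group intervention (sessions or home activity)? Ask it for every event in both arms.
2. State that the number of participants with any adverse event will be reported by arm regardless of attribution, and that any comparative safety statement will rest on this count. Present relatedness as supporting information.
3. Where feasible, give the panel case summaries with the allocation and arm-revealing wording removed.

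Items 1 and 2 are changes of wording; the panel already exists and the events are already to be recorded. Item 3 needs some editing before review, and some summaries will still reveal the arm.
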